**Study Title: Social and Relational Capital to Overcome Social Determinants of Health.**

**The community identified problem this project seeks to solve (380 characters):**  
**Describe Goals**

We look to implement the existing models created by The Open Table, Inc. to leverage social and relational capital and positively impact various Social Determinants of Health (SDOH) including: access to healthcare, healthcare outcomes (hospitalizations, ER visits, PCP visits), improve individual patient resilience. We further, look to positively impact burnout rates for providers that care for patients with difficult social barriers to care through enhanced community resources.

**Describe your work on the problem thus far. Outline current data and results. Describe any prior projects and, if applicable, any funding sources (2200 characters):**  

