**Describe the planned research approach including the community engagement approach (13,500 characters):**

**Describe approach**

We will partner with a Federally Qualified Health Center (FQHC) at Valleywise health to identify and recruit patients into the study. Valleywise health is the largest safety-net healthcare organization in Arizona, serving over 430,000 ambulatory visits per year. They serve a patient population that is medically complex with challenging social barriers to healthcare including homelessness, substance abuse, food insecurity, illiteracy, etc. The healthcare team (providers and social workers) are often challenged by limited community resources to assist patient's through SDOH challenges.

We aim to recruit 30 patients (total) into this study to power the results sufficiently. These patients will have an identified SDOH need that is negatively impacting their health (as determined by the FQHC staff). Once referred, the patient will be screened with a SDOH screening tool (the CMS Accountable Health Communities Screening Tool) to establish a

baseline and interviewed to determine their individual needs, they will also complete the Brief Resilience Survey (BRS) in addition to semi-structured qualitative interviews. Screening and interviews will take place by the study coordinator and/or researchers. Once accepted into the study, the study staff will refer the participant to a member of The Open Table to implement The Open Table model (Network Table) and measure specific outcomes over the intervention period. Patient name, phone number, and email will be shared with The Open Table in order for them to contact the participants and learn more about their SDoH needs. The Network Table consists of 10 trained volunteers that will meet bi-weekly to address the patient's SDoH needs, prioritize interventions and meet with the patients as is appropriate and necessary to resolve each identified need. Once the patient's needs have been met, a seat at the table will become available and additional patients will be recruited to the table. If additional needs arise for individual patients (and there is capacity at the table) patients are welcome to rejoin the table to address additional needs throughout the 12-month study period.

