We intend to implement community engagement in 2 ways. First, we will partner with a community organization/501c3 (The Open Table) to bring their model of leveraging social and relationship capital to the healthcare community. Second, we will partner with a Federally Qualified Health Center (FQHC) (Valleywise Health) to help patients with identified SDoH needs that would benefit from enhanced community-based resources. Additionally, we will partner with said FQHC to measure patient-specific impact (outcomes in relation to SDOH) and provider impact (measure impact on burnout).

Patients will be recruited to the study with the assistance of a research coordinator and in partnership with FQHC staff. This study will follow patients and providers (the healthcare team) for up to one-year post-enrollment, or until patient intervention is complete. Baseline data will be collected via structured individual patient interviews and by collecting baseline SDoH data via the CMS Accountable Health Communities Screening Tool, BRS tool. Screening data may be shared with The Open Table so they can better understand the needs of the participant. Once enrolled in the study, patients will be assigned to a Network Table of trained community volunteers that will support patients with a focus on overcoming SDoH needs to improve health. Each "table" of volunteers will be led by a project director, and each volunteer will be trained by The Open Table.

We will also recruit referring providers to the study (anticipate approximately 10 providers). These providers will be asked to complete the Maslach Burnout Index pre/post intervention.

Inclusion criteria: We will include patients that are age 18 or over with an identified SDOH need that impacts healthcare outcomes (identified by the healthcare team).

Exclusion criteria: non-english speaking patients, patients <18 years old, patients who are pregnant.

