Recruitment: Potential participants with SDOH needs that are negatively impacting their healthcare will be referred by the FQHC healthcare team. Patients meeting inclusion criteria will be referred to the research team. Recruiting providers will provide eligible patients with a flyer with the research team contact information, once the flyer is returned to the research team the patient will be contacted for consideration of enrollment and consent. The research team will obtain consent for all patients appropriate for participation in the study. Providers that refer patients to the study will be asked complete a survey of baseline and post-intervention burnout (Maslach burnout inventory).

Measures:

Our primary outcomes will be responses to the following survey questions pre/post intervention: CMS Accountable Health SDOH Screening Tool and the Brief Resilience Scale (BRS).

Secondary outcome measures will include: # of hospitalizations and # of ER visits, # of primary care visits and perceived access to nutritious food, healthcare worker and/or social worker burnout evaluations (pre/post). Additionally, we will complete semi-structured qualitative interviews of each participant pre/post to determine the impact of this intervention on other aspects of their life/health.

Tertiary measures will be provider burnout scores pre and post intervention based on the Maslach Burnout Inventory.

We will obtain baseline data on # of hospitalizations in the prior 12 months, # of ER visits in the prior 12 months, # of primary care visits in the prior 12 months through patient interviews and use of the EMR. Patients will have SDoH screening via the CMS Accountable Health Communities Screening Tool at baseline. Additionally, each enrolled patient will be interviewed at baseline to understand their responses to the primary outcome measurements. To better understand the patient-specific variables that may contribute to SDoH challenges and outcomes we will also collect patient demographics (e.g., age, gender, race, ethnicity, marital status), medical information (e.g., medical comorbidities, current medications), socioeconomic status (e.g., education, income, employment), environmental data (e.g., address, census measures). Provider surveys will be collected using the Maslach Burnout Inventory.(pre and post intervention). These data will be collected via the electronic medical record, survey data from patients, and survey data from medical providers and healthcare staff.

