#### Statistical Analysis:

Primary outcomes will be measured by:

Difference in proportion (before vs after intervention) in SDOH status and resilience score.

Secondary outcomes will be measured by:

Difference in number of hospitalizations in the 12 months before vs 12 months during intervention, difference in number of ER visits in the 12 months before vs 12 months during intervention, difference in number of primary care visits in the 12 months before vs 12 months during intervention, difference in proportion (before vs after intervention) of patients answering that they perceive they have access to nutritious food, difference in proportion (before vs after intervention) of patients answering that they perceive they have access to nutritious food.

Baseline patient demographics and clinical characteristics will be descriptively summarized. Differences in categorical endpoints before vs after the intervention will be tested using McNemar's test for paired proportions, or exact McNemar's test for small sample sizes. Differences in continuous endpoints before vs after the intervention will be tested using paired t-tests, or appropriate non-parametric test.

The semistructured interview (qualitative data) will be analyzed separately for significant impact, trend and analysis.

Provider data that are recruited for analysis of burnout will be analyzed in difference in proportion to responses pre/post on the Maslach Burnout Inventory. Given the # (10) of participants in this section, we do not expect to reach statistical significance (due to inadequate power) but we will use this as an exploratory outcome.

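### The 12-month baseline for hospitalizations and ER visits is likely to contain some of the events that prompt referral, so the paired difference can show a fall with no programme effect

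*Combined protocol and SAP*

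**What the plan says.** Under Statistical Analysis, the secondary outcomes include "Difference in number of hospitalizations in the 12 months before vs 12 months during intervention" and "difference in number of ER visits in the 12 months before vs 12 months during intervention". Both compare the same patients by a paired t-test or a non-parametric alternative. The measures text under Describe approach fixes the baseline: "We will obtain baseline data on # of hospitalizations in the prior 12 months, # of ER visits in the prior 12 months", taken from interviews and the EMR.

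Entry depends on staff judgement. Describe approach says "These patients will have an identified SDOH need that is negatively impacting their health (as determined by the FQHC staff", and the recruitment text says "Potential participants with SDOH needs that are negatively impacting their healthcare will be referred by the FQHC healthcare team". The inclusion criterion asks for an "identified SDOH need that impacts healthcare outcomes (identified by the healthcare team". The Describe Goals section spells the term out as "healthcare outcomes (hospitalizations, ER visits, PCP visits".

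There is no comparison group: "Once enrolled in the study, patients will be assigned to a Network Table of trained community volunteers". No earlier baseline period is planned, and regression to the mean is not mentioned.

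**The concern.** Selection happens at the end of the baseline window, and the entry criterion is worded in terms of outcomes that include the two counts later analysed. A patient just admitted or seen in the ER is plausibly more likely to be noticed and referred. The baseline year would then hold those prompting events while the following year returns to the patient's usual level.

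The Describe Outcomes section expects fewer hospitalizations and ER visits and presents the project as proof of concept for other populations. A fall produced by the timing of referral would be read as benefit.

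This is narrower than the general lack of a control group. It concerns where the baseline window sits, and it can be examined within the single group by looking at an earlier window.

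**Working it through.** **Plan's own figure.** There is none for these counts. The Power Analysis covers only the primary before/after proportions at 30 patients.

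**Inputs from the documents.** Twelve months before against twelve months after, same patients, no comparator, entry by staff judgement.

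**Inputs assumed.** Each patient has a constant yearly event rate, drawn from a gamma distribution with mean m = 0.5 to 2 and shape k = 0.5 to 1. Counts are Poisson. A patient with at least one event in the last h years before referral is W = 2, 3 or 5 times as likely to be referred. There is no programme effect.

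**Formulas.** Let r = k/(k + m·h).

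- Chance of no event in the trigger period: r^k
- Normalising term: D = r^k + W(1 − r^k)
- Yearly count outside the trigger period, among referred patients: A = [W·m − (W − 1)·m·r^(k+1)]/D
- Count inside the trigger period: T = W·m·h/D
- Planned baseline: B = T + (1 − h)·A. The year after has mean A. False fall = 1 − A/B.

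**Example: m = 1, k = 1, W = 3, trigger 3 months (h = 0.25).**

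- r = 1/1.25 = 0.80; D = 0.80 + 3 × 0.20 = 1.40
- A = (3 − 2 × 0.64)/1.40 = 1.229
- T = 0.75/1.40 = 0.536
- B = 0.536 + 0.75 × 1.229 = 1.457
- False fall = 1 − 1.229/1.457 = 15.7%

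In a simulation of 30-patient trials at these settings, a paired t-test gave a two-sided 0.05 significant fall in roughly 11% to 12% of trials, against a nominal 2.5% in that direction.

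**Range over k and W, 3-month trigger.**

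| Mean events per year | False fall, planned baseline |
|---|---|
| 0.5 | 12% to 30% |
| 1 | 9% to 21% |
| 2 | 5% to 12% |

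With W = 1 (recent use does not affect referral), D = 1 and A = B = m, so the false fall is 0%.

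**A different referral model.** Let any event in the whole prior year raise referral two-fold to four-fold, with shapes 0.5 to 2. Hospitalizations (mean 0.5) fall falsely by 18% to 38%, and ER visits (mean 1.5) by 6% to 14%.

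**Would an earlier window help?** With m = 1, k = 1, W = 3:

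| Trigger period | Mean after | Planned baseline: mean, false fall | Months -15 to -4: mean, false fall | Months -24 to -13: false fall |
|---|---|---|---|---|
| 3 months | 1.229 | 1.457, 15.7% | 1.229, 0% | 0% |
| 6 months | 1.267 | 1.533, 17.4% | 1.400, 9.5% | 0% |
| 12 months | 1.250 | 1.500, 16.7% | 1.438, 13.0% | 0% |

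For the 6-month row, three of the twelve months in the -15 to -4 window still lie in the trigger period, where the yearly rate is 1.8: 0.25 × 1.8 + 0.75 × 1.267 = 1.400. Across means 0.5 to 2 and shapes 0.5 to 1 at W = 3, months -15 to -4 leave a false fall of 4% to 16% with a 6-month trigger and 5% to 24% with a 12-month trigger.

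**If personal rates drift.** With monthly rates autocorrelated at 0.80 to 0.98 (mean 1, shape 1, W = 3, 3- or 6-month trigger), months -24 to -13 show a false rise of about 2% to 7%. That error runs against the programme.

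**The case against.** Entry is by social need, not by event count. No passage requires or names a recent admission or ER visit, and the needs listed (homelessness, substance abuse, food insecurity, illiteracy) can be long-standing. A reader might infer that recent events are the stated reason for referral, so that a fall is certain. The documents do not support that: the link is an inference from the inclusion wording and the goals, and the bias vanishes if recent use plays no part. This stands, and the conclusion is conditional for that reason.

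A reader might also infer that skipping the three months before referral cures the problem. That holds only if the trigger period is three months or less, and the documents give no such period. This stands too, and it is why the earlier year must be the lead check.

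The stakes are limited: these are secondary outcomes with no power claim, in a preliminary study with a feasibility aim. That argues for a sensitivity analysis rather than a redesign. It does not remove the need, because the plan already anticipates these reductions as project results.

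**Conclusion.** The concern holds conditionally. The baseline year is likely to contain some prompting events, because the inclusion criterion refers to outcomes that the plan itself lists as including hospitalizations and ER visits. If recent use raises the chance of referral, the planned paired difference shows a fall with no programme effect: about 5% to 30% under the constant-rate model with a 3-month trigger and a two- to five-fold referral preference. The event rates, their spread, the referral preference and the trigger length are all assumptions, so the percentages illustrate scale and do not predict this study's result.

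The calculation assumes full 12-month windows on both sides. Describe approach also lets follow-up end when the intervention is complete; a count confined to a shorter period would add to any apparent fall, and those passages should be reconciled separately.

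**What to change.** In the measures text of Describe approach and in Statistical Analysis:

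- Extract EMR hospitalization and ER counts by month for 24 months before referral. State where the interval between referral and enrolment is counted.
- Keep the planned comparison.
- Pre-specify a sensitivity comparison of the 12 months after enrolment with months -24 to -13 as the lead earlier baseline. Add months -15 to -4 as a secondary one, stating that it removes the bias only for a trigger period of three months or less.
- Use EMR counts on both sides, in patients whose record covers the window, and report how many are excluded.
- Attribute a reduction to the programme only if the estimated fall against months -24 to -13 is in the same direction and of similar size, reported with its confidence interval. Say in advance what counts as similar. No second significance test is needed. Otherwise report both counts as descriptive.

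This deals with selection at referral only, not with other limits of a single-group design.

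Cost: twelve more months in an EMR extract already planned for 30 patients, and a short SAP addition. Some patients will lack a 24-month record, EMR-only counts miss care elsewhere, the earlier window may understate a real effect if personal rates drift, and the result may look less favourable.

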**Describe Preliminary Data**

The Open Table is an existing 501c3 that establishes support "tables" of trained volunteers and community leaders (table members) that help individuals (friends) with an identified need (housing insecurity, food insecurity, access to healthcare problems, etc.) They accomplish this through the concept of leveraging social and relationship capital to problem solve with the friend. Data from an existing project/collaboration with Anthem Blue Cross has demonstrated the following outcomes for a group of 20 mothers with substance use disorder (SUD): 156% increase in relationships, 50% reduction in hospitalizations, 64% increase in drug sobriety, 40% increase in alcohol sobriety, 67% increase in stable housing, 46% increase in food security, 60% increase in employment. This project was 18-months long and all data was collected using The Accountable Health Communities Screening Tool.

Prior to joining Mayo Clinic, the principle investigator ([name]) worked at a Federally Qualified Health Center (FQHC) as an Internal Medicine Physician at Valleywise Health. Patients in this population suffer disproportionately from healthcare disparities as a result of barriers to Social Determinants of Health (SDOH). Further, healthcare workers in this setting often experience burnout from being unable to adequately help patients through complex, multifactorial SDOH issues that negatively impact their health.

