**Aim 1: Determine the feasibility of implementing The Open Table model at a FQHC.**

Hypothesis: None

**Aim 2: Examine the impact of The Open Table model on social determinants of health in a healthcare setting with specific interest in access to care, hospitalizations, and social connectedness, individual capacity-building.** We will collect pre-implementation data via structured interviews and SDoH data via the CMS Community Health Social Needs Screening tool on patients enrolled in this study to identify various metrics of SDoH including baseline number of hospitalizations and number of ER visits within the previous year, perceived social support, access to food, housing, primary care visits. We will follow patients longitudinally as we implement the Open Table model of volunteers paired with a patient to determine the impact of social and relationship capital on these outcomes. Post-intervention survey data and interviews will be collected to measure impact. Hypothesis: Social support and enhanced relationships through the Open Table model will lead to reduced SDoH.

**Aim 3: Examine the impact of enhanced community-based resources (The Open Table) on healthcare providers and social services personnel (the healthcare team) satisfaction.**

Specifically, we will be looking at the healthcare team's ability to deliver care and perceived satisfaction in caring for patients with a SDOH needs. Pre and post implementation data will be collected via the Maslach Burnout Inventory tool. We will examine structural and system-level barriers to healthcare delivery for patients with an identified SDOH need and explore the value and impact of The Open Table in these situations.

Hypothesis: Enhanced healthcare provider access to community-based resources through The Open Table model will lead to improved healthcare delivery, enhanced satisfaction and reduced burnout on the healthcare team for providers caring for patients with a SDOH need in an FQHC setting.

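### With no minimum time at the clinic, the before/after comparison of primary care visits could credit the Open Table with a rise caused by recently joining the FQHC

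*Combined protocol and SAP*

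**What the plan says.** All places are in the combined protocol and SAP.

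- **Eligibility** (Describe approach, inclusion and exclusion criteria): "We will include patients that are age 18 or over with an identified SDOH need that impacts healthcare outcomes". The only exclusions are these: "Exclusion criteria: non-english speaking patients, patients <18 years old, patients who are pregnant". Nothing concerns how long a patient has been with the clinic.
- **Route of entry** (Describe approach, Recruitment): "Potential participants with SDOH needs that are negatively impacting their healthcare will be referred by the FQHC healthcare team".
- **Data source** (Describe approach, Measures): the baseline is the number "of primary care visits in the prior 12 months through patient interviews and use of the EMR".
- **Analysis** (Statistical Analysis, secondary outcomes): the "difference in number of primary care visits in the 12 months before vs 12 months during intervention", tested by a paired t-test or a non-parametric alternative. No control group is described, and there is no adjustment or stratification for time at the clinic.
- **Intended reading** (Aim 2): patients are followed to "determine the impact of social and relationship capital on these outcomes".

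**The concern.** Everyone enters through the FQHC, so everyone has reached the clinic before enrolment. For an established patient, both years are spent with the same access to the clinic. For a patient who joined a few months before enrolment and had little primary care earlier, most of the baseline year precedes that access and the whole of the following year comes after it. Visits would then rise with no contribution from the Table.

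Interviewing patients as well as reading the EMR helps only in part. It can recover visits made elsewhere, but not visits that never took place, so a perfectly recorded baseline can still be low.

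Access to care is a named interest of Aim 2, and the primary care count is the utilization measure closest to it. A rise could be reported as better access due to the Table when registration at the clinic produced it.

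**Working it through.** **The plan's own figure.** The documents give no expected value or power for primary care visits. The statement of at least 80% power in the Power Analysis concerns the two primary before/after proportions, and this point does not touch it.

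**Inputs from the documents.** 30 patients, one group, two 12-month counts, paired t-test, alpha 0.05 (taken as two-sided).

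**Assumed inputs, none of which is in the documents.**
- λ: visits per year once in the clinic (4; range 3 to 6)
- f: share of patients who joined within the past year (10% to 50%)
- τ: mean fraction of the baseline year already spent in the clinic (0.25 if joining is uniform over the last 0–6 months; 0.5 if over 0–12 months)
- r: visit rate before joining, as a fraction of λ, all of it captured (0 or 0.5)
- The Table's effect is zero.

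**Expected spurious change.** The mean baseline count is λ[(1 − f) + f(τ + (1 − τ)r)] and the mean count during the intervention is λ. The difference is λ · f · (1 − τ) · (1 − r).

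Rejection rates come from simulating the paired t-test with 30 patients. Counts were Poisson, with gamma variation between patients (variance 0.5 on the rate multiplier). Separate runs differ by a point or two.

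| Joining, earlier care | f | Arithmetic (λ = 4) | Mean rise | Trials significant |
|---|---|---|---|---|
| 0–6 months, none | 10% | 4 × 0.10 × 0.75 | 0.3 | about 8% |
| 0–6 months, none | 30% | 4 × 0.30 × 0.75 | 0.9 | about 31% |
| 0–6 months, none | 50% | 4 × 0.50 × 0.75 | 1.5 | about 68% |
| 0–12 months, none | 10% | 4 × 0.10 × 0.5 | 0.2 | about 6% |
| 0–12 months, none | 50% | 4 × 0.50 × 0.5 | 1.0 | about 39% |
| 0–12 months, half rate | 10% | 4 × 0.10 × 0.5 × 0.5 | 0.1 | about 5% |
| 0–12 months, half rate | 30% | 4 × 0.30 × 0.5 × 0.5 | 0.3 | about 8% |
| 0–12 months, half rate | 50% | 4 × 0.50 × 0.5 × 0.5 | 0.5 | about 15% |

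In the 30% case with joining over 0–6 months and no earlier care, 3 to 6 visits a year give a rise of 3 × 0.30 × 0.75 = 0.7 to 6 × 0.30 × 0.75 = 1.4 visits, significant in roughly 25% to 38% of trials. If f = 0, or if earlier care elsewhere ran at the same rate and was fully captured (r = 1), the expected change is 0 and the rate is about 5%.

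**Adding the referral visit.** If the contact at which each patient is referred is a primary care visit and counts at baseline, 1 is subtracted from each mean difference. For joining over 0–6 months with no earlier care:
- 10% joiners: 0.3 − 1 = −0.7
- 30% joiners: 0.9 − 1 = −0.1
- 50% joiners: 1.5 − 1 = +0.5

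A significant rise then occurs in almost no trials, about 1% and about 8% respectively. At 10% joiners a significant fall occurs in about 25%.

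**Restricting to established patients.** At 30% joiners, 30 × 0.7 = 21 pairs remain. With the referral visit excluded, the false-positive rate is about 5%. With it counted, there is a spurious fall of 1.0 visit, significant in about 36% of trials.

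**The case against.** The strongest case on the other side has four parts.

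1. **The size is assumed.** No section gives the share of recent joiners, their earlier care or their visit rate. The largest figures combine very recent joining with no earlier care at all. This stands, and it is why a range is given.
2. **The referral contact pushes the other way.** One such visit per patient roughly cancels the 30% case above. One for everybody is an upper assumption, since a social worker may refer, but zero is the opposite extreme. Referral during a spell of heavy use would also lower the later count. This stands as to direction. It does not make the comparison sound, because two biases that happen to offset still leave the result uninterpretable.
3. **The link to access needs is inferred.** The Preliminary Data section says that the organization's tables "help individuals (friends) with an identified need (housing insecurity, food insecurity, access to healthcare problems, etc". That describes its general work and is not an entry criterion here, and an established patient can also have an access problem. This stands. The point needs only that recent joiners are admissible, which the eligibility text shows.
4. **It is one secondary outcome in a small preliminary study.** The plan states no hypothesis that primary care visits will rise. This limits the importance of the point but does not remove it.

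A reader might infer that the comparison will show a spurious rise. The documents do not support that: the share of joiners is unknown and opposing features are present. Nor can it be said that restricting to established patients is enough by itself, since that holds only if the referral visit also leaves the baseline count.

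**Conclusion.** The concern holds as a possible bias. Nothing in the plan keeps out recent joiners, records when they joined, or separates joining the clinic from the Table in a single-group comparison. The spurious rise runs from about 0.1 visits, with a false-positive rate barely above 5%, to about 1.5 visits and 68%. That range rests on 4 visits a year, 10% to 50% joiners and no referral visit counted. It is nil if earlier care elsewhere was equal and fully captured. Because a counted referral visit works in the opposite direction, the net sign is not established. The primary outcomes and the stated power are unaffected. The change is worth making because it is cheap and because, without a rule set in advance, any later restriction would look post hoc.

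**What to change.** - **Describe approach, Measures:** record from the EMR the date of each patient's first Valleywise primary care visit.
- **Statistical Analysis:** keep the all-patient comparison of primary care visits. Add a pre-specified comparison limited to patients whose first visit was at least 12 months before enrolment. Leave the referral visit out of the baseline count in both.
- **Recent joiners:** report them separately and descriptively, as visits per month from first visit to enrolment and visits per month after enrolment.
- **Interpretation:** attribute a rise in primary care visits to the Table only if it is also seen in the established patients.

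The cost is one date from a record that is already a data source, plus a few sentences of text. Eligibility and recruitment do not change. The restricted comparison has fewer pairs (21 of 30 if 30% are recent joiners), for one secondary outcome only. Patients who return after a lapse in care can meet the 12-month rule and still have a low baseline, so they are not fully handled.

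### Provider burnout is collected as a score but analysed as an undefined proportion, which gives up most of the power that about 10 score pairs have for a large change

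*Combined protocol and SAP*

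**What the plan says.** Under Measures, in the approach section, the provider outcome is a score: "Tertiary measures will be provider burnout scores pre and post intervention based on the Maslach Burnout Inventory". The same list already has "healthcare worker and/or social worker burnout evaluations (pre/post") among the secondary outcomes. The approach section puts the group at about 10: "We will also recruit referring providers to the study (anticipate approximately 10 providers").

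The Statistical Analysis section changes the quantity: "Provider data that are recruited for analysis of burnout will be analyzed in difference in proportion to responses pre/post on the Maslach Burnout Inventory". It gives no cut-off, subscale, response category or test for that proportion. It then says of the 10 participants that "we do not expect to reach statistical significance (due to inadequate power) but we will use this as an exploratory outcome".

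The same section has two general rules. Categorical endpoints are "tested using McNemar's test for paired proportions, or exact McNemar's test for small sample sizes". For scores, "Differences in continuous endpoints before vs after the intervention will be tested using paired t-tests, or appropriate non-parametric test".

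**The concern.** The outcome and its analysis do not match. A score measured twice in the same person calls for a within-person change, and the plan already has a rule for that. The provider sentence uses a proportion instead and gives no reason.

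Two things follow. First, the proportion cannot be computed from the plan: someone must choose a subscale and a cut-off, possibly after seeing the data. Second, a provider whose score falls but stays on the same side of the cut-off contributes nothing to a paired test of proportions. With 10 pairs that loss can be severe.

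What is at stake is the information for Aim 3. Its hypothesis includes reduced burnout in the healthcare team, and the Maslach inventory is the only provider instrument the plan names. The outcome also appears as secondary, tertiary and exploratory in different places, so the weight of any result is not fixed in advance.

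**Working it through.** The plan gives no power figure for providers, so there is none to reproduce. Its only numerical power statement concerns the 30 patients.

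**Inputs from the plan.** n = 10 pairs; exact McNemar for categorical endpoints in small samples; paired t or a non-parametric test for continuous endpoints; alpha 0.05 (stated for the patient outcomes).

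**Assumed, not in the plan.** Two-sided testing; bivariate normal pre and post scores with equal SD; pre/post correlation r of 0.3 to 0.8; baseline share above the cut-off of 40% to 70%.

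**Step 1: what exact McNemar needs.** With b providers crossing down and c crossing up, the two-sided p-value is 2 × P(X ≤ min(b, c)), X ~ Binomial(b + c, 0.5).

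- 5-0: 2 × 0.5^5 = 0.0625
- 6-0: 2 × 0.5^6 = 0.031
- 7-1: 2 × (1 + 8)/2^8 = 0.070
- 8-1: 2 × (1 + 9)/2^9 = 0.039

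So at least 6 of 10 must cross with none going the other way, or at least 8 with one going the other way. If nobody moves the wrong way and each provider crosses with probability π, power is P(Binomial(10, π) ≥ 6): 17% at π = 0.4, 38% at 0.5, and 80% only at about π = 0.67.

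**Step 2: power of the paired t-test.** Noncentral t with 9 degrees of freedom and noncentrality √10 × δ, where δ is the mean change in SDs of the differences. Power is 29% at δ = 0.5, 62% at 0.8, 80% at 1.0 and 92% at 1.2. Simulated Wilcoxon signed-rank power is close: about 78% at δ = 1.0.

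**Step 3: both tests on the same change.** In units of the score SD the shift is δ × √(2(1 − r)). The probabilities of crossing down and up follow from the bivariate normal, and power is the trinomial probability of the outcomes in Step 1 with p<0.05.

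Example with δ = 1.0, r = 0.5 and baseline share 50%: the shift is 1.0 × √(2 × 0.5) = 1.0 SD, so the share above the cut-off falls from 50% to 16%. The chance of crossing down is 37.3% and of crossing up 3.1%. Exact McNemar power is 10.4%, against 80% for the t-test.

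Over baseline shares of 40-70%, exact McNemar power is:

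| Correlation | δ = 0.5 (t-test 29%) | δ = 1.0 (t-test 80%) |
|---|---|---|
| 0.3 | 2.4-4.4% | 8-27% |
| 0.5 | 1.3-2.2% | 6-16% |
| 0.7 | 0.4-0.7% | 3-6% |
| 0.8 | 0.2-0.3% | 1-3% |

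**Step 4: precision of the score analysis.** With 10 pairs, the 95% CI for the mean change has half-width 2.262/√10 = 0.72 SD of the differences. That is wide, but it is an interval on the scale that was measured.

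**The case against.** The strongest reply is that the plan already concedes the point: it expects no significance, puts this down to low power, and calls the outcome exploratory. That stands as to weight, since no primary conclusion, sample size or error rate depends on burnout. It does not explain why scores should become an undefined proportion, which adds to the loss.

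The provider sentence names no test. Exact McNemar is inferred from the general rule for categorical endpoints, and the rule for continuous endpoints could be read as covering the scores. This also stands, so the McNemar figures are conditional. An uncorrected asymptotic McNemar test would reach 33-50% at δ = 1.0 and r = 0.5, still well below 80%, although the plan's small-sample wording points to the exact test.

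Three stronger readings are tempting, and the documents do not support them.

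- *The analysis could not show any change.* At δ = 1.2, r = 0.3 and a baseline share of 70%, exact McNemar reaches about 40%.
- *It would leave no usable estimate of size.* A paired difference in proportions is an estimate and can carry an interval, though a wide one at n = 10. The plan does not say that scores will go unreported.
- *The plan is wrong to blame the 10 participants.* At δ = 0.5 the t-test has only 29% power, so for modest changes that explanation is right. Dichotomising is the larger cause only for changes near 0.8-1.2 SD of the differences, and the documents give no reason to expect changes that large.

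The secondary entry (healthcare or social workers) and the tertiary entry (providers) might be two groups. However, the approach section recruits only referring providers for the inventory, so the labels still need reconciling.

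**Conclusion.** The point holds as a minor one. The mismatch between a score in the Measures text and an undefined proportion in the Statistical Analysis section is in the text and rests on no assumption. The requirement for six one-way crossings is exact, given n = 10 and exact McNemar.

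The size of the loss depends on the assumed correlation, cut-off and normality, and on applying the exact test. At a change of 1.0 SD of the differences it is about 80% power against roughly 1-27%. At 0.5 SD it is 29% against 0.2-4%, where neither analysis is adequate. The outcome should stay exploratory under either analysis.

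**What to change.** In the Statistical Analysis section, replace the provider sentence with wording such as: 'Provider burnout will be analysed as the within-provider change (post minus pre) in the Maslach Burnout Inventory score, reported as the mean paired change with a 95% confidence interval, using a paired t-test or Wilcoxon signed-rank test. One subscale, named here in advance, is principal; the others are reported descriptively. Any proportion above a pre-specified cut-off is descriptive only.'

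Under Measures, list provider burnout once, as exploratory, and state whether social workers belong to the same group.

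The cost is a few sentences, with the same data and no extra collection. The one small downside is that the team must commit to a principal subscale, which also avoids several unranked tests in 10 people.
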